2.6 STATISTICAL ANALYSIS AND DISSEMINATION

The DCC will be primarily responsible for statistical analysis of the research questions posed by VEST. The data will reside with the DCC and will be analyzed by DCC personnel for interim DSMB reports and for publications, presentations and other dissemination activities according to the plan described in section 1.5.11 and with scientific oversight by the Steering Committee.

AF	Atrial Fibrillation
AHA	American Heart Association
CABG	Coronary Artery Bypass Grafting surgery
CCC	Clinical Coordinating Center
CCU	Coronary Care Unit
CHF	Congestive Heart Failure
CMS	Centers for Medicare Services
CRF	Case Report/Record Form
CRT	Cardiac Resynchronization Therapy
DCC	Data Coordinating Center
DI	Detection Interval
DSMB	Data Safety Monitoring Board
ECG	Electrocardiogram
EF	Ejection Fraction
FVT	Fast VT
HRV	Heart Rate Variability
ICD	Implantable Cardioverter Defibrillator
IRB	Institutional Review Board
ITT	Intent-to-Treat
MI	Myocardial Infarction
MVP	Minimal Ventricular Pacing
NIH	National Institutes of Health
NHLBI	National Heart, Lung and Blood Institute
NID	Number of Intervals to Detect
NIPS	Non-invasive Programmed Stimulation
NSVT	Non Sustained Ventricular Tachycardia
QOL	Quality of Life
RNID	Number of Intervals to Redetect
PCI	Percutaneous Coronary Intervention
SVT	Supraventricular Tachycardia
VF	Ventricular Fibrillation
VT	Ventricular Tachycardia

VEST Statistical Analysis Plan

Version 1.0 to Version 1.1 (5/12/2012)

1. Primary endpoint revised from sudden cardiac death to sudden cardiac death or nonsudden death to ventricular arrhythmia (Section A, page 1).

Version 1.1 to Version 1.2 (12/5/2016)

- 1. Analysis of primary endpoint revised to use a simple chi-square test rather than exact stratified methods (Section A, page 1).
- 2. Section on Exploratory Analysis of Compliance added (Section B.4, page 2).

Version 1.2 to Version 1.3 (3/2/2017)

1. Plan is added for weighted sensitivity analysis of primary outcome omitting patients with indeterminate cause of death or unknown vital status (Section B.1.3)

VEST Statistical Analysis Plan

A. Primary Analysis

Treatment effects on the primary outcome, sudden death or non-sudden death due to ventricular arrhythmia, will be assessed using a chi-square test to compare incidence proportions in the VEST and control groups at 60/90 days after randomization. The test of the primary null hypothesis of no treatment effect will be conducted using a two-sided alpha of 5%. This analysis will be by intention to treat (ITT), according to treatment assignment, without regard to adherence to the assigned study intervention or other aspects of care.

B. Secondary Analyses

B.1. Sensitivity Analyses

Results will be checked for robustness in three planned sensitivity analyses.

1. Modified intention to treat. We will omit from this analysis, patients who do not survive until discharge from the index hospitalization, and the 60/90 day follow-up will begin at the later event of randomization or discharge. The rationale is that the vest is essentially never worn in hospital, and so can provide no protection until after discharge. Although mortality is highest soon after a serious MI, close in-hospital monitoring is expected to keep the in- hospital death rate low. As part of this analysis, we will characterize times from randomization to discharge using histograms, stratified by group.

2. Adjustment for baseline imbalances. If we find substantial imbalances in powerful baseline prognostic variables with the potential to confound treatment assignment meaningfully, we will perform a sensitivity analysis using a logistic regression model to adjust for these factors. If more than two factors need to be adjusted for, we will summarize them using propensity scores [Rosenbaum 1983], then use a logistic model to adjust for the scores as a three-knot cubic spline, requiring two basis functions, so that the conservative rule of thumb of approximately 10 events per variable is observed [Vittinghoff 2006].

3. Inverse weighting to deal with indeterminate cause of death and missing vital status. In the primary analysis, participants with indeterminate cause of death or missing vital status will be assumed not to have had a primary study event. In two secondary analyses, we will restrict the analysis to deceased participants with determinate cause of death and those known to be alive, weighting these observations so that their baseline correlates of the primary outcome are representative of the entire randomized cohort. To do this, we will develop two logistic models: the first for having determinate cause of death among all patients known to have died, and the second for having known vital status among all participants. Weights will be calculated as the inverse of the product of the fitted probabilities from these two models, after assigning a fitted probability of 1 from the first model for patients known to be alive. Variables in each model will be selected, without regard to the primary outcome, from a list of known correlates of the primary study outcome, as specified by Drs. [name], [name], and [name]. To deal with missing values of the candidate variables in the *a priori* list, multiple imputation will be used, followed by averaging of the weights obtained from each of ten completed datasets. Two versions of this sensitivity analysis will be conducted, the first excluding and the second using information from the vest in

determining vital status. The weighted analyses will use procedures properly accounting for the slightly smaller sample size available for analysis.

B.2. Heterogeneity of treatment effects

• By randomization stratum. We will use a logistic model to assess heterogeneity of the treatment effect across the 6 randomization strata jointly defined by EF, PCI, and CABG, as well as across the 2 strata defined by EF and the 3 strata defined by PCI and CABG. Nominal differences across strata will be conservatively interpreted in the light of tests for interaction between treatment and stratum, using a Bonferroni-corrected two-sided alpha of 0.05/3=0.0167. In additional exploratory analysis, we will assess modification of the ITT treatment effect by drugs, NYHA class, BMI, gender, and compliance

B.3. Treatment effects on secondary endpoints

• *Total mortality, revascularization, ICD implantation*. Treatment effects on these binary secondary endpoints will be analyzed using chi-square tests, as proposed for the primary analysis. Logistic regression will be used to adjust for baseline imbalances as needed.

• *Re-infarctions and hospitalizations*. Treatment effects on these potentially recurring outcomes will be analyzed using the Anderson-Gill extension of the Cox model for recurrent events, with robust standard errors [Therneau 2000], to account for potential clustering of recurrent outcomes within participants.

 Vest-related symptoms. Fisher's exact tests will be used to compare frequency of potentially vest-related symptoms currently tabulated in the DSMB report, including fatigue, back pain, trouble sleeping, and upper body rash and itching.

B.4. Exploratory analysis of compliance

Factors associated with compliance with the VEST will be examined in an exploratory, hypothesis- generating analysis focusing on seasonality, site, geographic region, body mass index (BMI), time on study, baseline EF, as well as age, gender, race/ethnicity, education, marital and employment status, NYHA Class, and length of hospital stay. The analysis will use two-part models for repeated daily compliance measures, the first a GEE logistic model for any use of the VEST, and the second a GEE linear model for hours of use, transformed as necessary to meet normality assumptions, for patient-days where any use is detected. Inference for the combined effects of each proposed covariate on both elements of compliance (any use and hours of use among users) will be implemented using the seemingly unrelated estimation strategy. [Weesie, 1999]

C. References

- Weesie, J. 1999. sg121: Seemingly unrelated estimation and the cluster-adjusted sandwich estimator. Stata Technical Bulletin 52: 34–47. Reprinted in Stata Technical Bulletin Reprints, vol. 9, pp. 231–248. College Station, TX: Stata Press.

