1.5.4 Schedule and Description of Participant Visits

Each of the study

participants will be first seen in the hospital during their admission for MI or after discharge in the clinic within the window of enrollment. They will then be followed with one phone call and one clinic visit. The schedule for testing and data collection is outlined in Table 2. The visit timeline and windows for visits are provided in Chapter 3 of the Operations Manual.

• *Enrollment Visit (V0):* Begins during the participant's hospitalization for MI
 Table 2: Scheduled visits and data collection

DATA COLLECTED AND		VISITS			
TESTING PERFORMED		Post-discharge			
	V0	V1	V2	Registry	
	Enrollment	1 Month Phone	3 Month Visit		
Screening and Medical History	Х				
Vital signs, discharge meds & diagnoses (from chart)	X				
Symptom Checklist		Х	Х		
Medication Review	Х	Х	Х		
Medical Care Utilization		Х	Х	Х	
Vital Status			Х	Х	
QOL Survey			Х		
Test Reports 12 lead ECG Local Labs 	From Medical Record				
Echocardiography	From Medical Record		From Medical Record	From Medical Record	
Home Monitoring LifeVest 	upload baseline at fitting		in 1 st week, 1 weekly		

or within the window of enrollment after discharge. Participants who meet enrollment criteria will be asked to participate in the study after they are medically stable. After consent for VEST, they will be enrolled and randomized to vest or no vest. If randomized to vest, they may leave the hospital with the vest. The enrollment visit will involve collection of information and data abstracted from the hospital chart.

- *1 Month Follow-up Telephone Call (V1)*: All participants will be contacted by phone to gather follow-up data. Participants will be asked about changes in medication, intervening hospitalization or visits to the emergency department, any problems with the vest (if randomized to the LifeVest) and a simple symptom checklist.
- *3 Month Visit (V2):* All participants will be seen for clinical data collection/final visit. Participants will be asked about changes in medication, intervening hospitalization or visits to the emergency department, any problems with the vest (if randomized to the LifeVest), and a simple symptom checklist. The patient's most recent EF will be extracted from his/her medical record and assessment of qualification for primary prevention ICD will also be recorded. A Quality of Life survey will be

Protocol

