1.5.6 Randomization

Participants will be randomized in a 2:1 ratio to either receive the LifeVest or not, respectively. Randomization will be stratified and blocked to protect against chance maldistribution of important predictors. Stratification will be by ejection fraction ($\leq 25\%$ vs. > 25%) and by revascularization status (i.e., None/PCI/CABG), both known strong predictors of mortality, and by clinical site to protect against maldistribution of other unmeasured potential confounders that might be unequally distributed at different clinical sites. Randomization blocks will vary in size to protect against *predictability* of randomization assignment within clinical site/EF/revascularization strata. Block size will vary from 3 to 6, allowing for a maximum absolute deviation of 4 participants from the exact 2:1 ratio in any given site/EF/revascularization stratum. Separate tables for each stratum will be pre-generated (by existing routines developed by the Senior Statistician for the study), encrypted, and accessible only to the Senior Statistician and the DCC Data Analyst.

The DCC will implement a web-based interface that clinical sites will use to obtain randomization assignments for each enrolled participant after completion of the Enrollment Visit. Clinical sites will access the randomization website using a secure password, and will be prompted to attest that all entrance criteria are met and that informed consent has been obtained. Each inclusion and exclusion criterion will require active attestation to minimize errors of omission. Once entry criteria are verified electronically, the recruiter will be shown a "randomize" button, and will receive the assignment ("Wear LifeVest" or "Do Not Wear LifeVest") upon activating the button since participants and clinical site clinicians are not blinded to treatment assignment. After randomization, the group assignment may be printed by the clinical sites from the website along with group-specific study instructions for physicians and participants.

If there is any question regarding eligibility for randomization, the clinical site personnel will contact the CCC for adjudication prior to seeking randomization. Every effort will be made to minimize protocol deviations regarding participant eligibility for the study, including quality control procedures to assure that the ejection fraction (EF) entry criterion is accurate.

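### Covariate adjustment depends on observed arm imbalance, with no threshold or candidate list, and the SAP keeps no fixed estimate adjusted for EF and revascularization

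*Combined protocol and SAP*

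**What the plan says.** - **Primary test.** In SAP section A the primary outcome "will be assessed using a chi-square test to compare incidence proportions in the VEST and control groups at 60/90 days after randomization". The test is unadjusted, by intention to treat, at two-sided 5%. The SAP change log for version 1.2 records that this replaced exact stratified methods.
- **Adjusted analysis of the primary outcome.** SAP B.1 item 2: "If we find substantial imbalances in powerful baseline prognostic variables with the potential to confound treatment assignment meaningfully, we will perform a sensitivity analysis". The model is logistic. Its form depends on how many factors are found: "If more than two factors need to be adjusted for, we will summarize them using propensity scores". The score then enters as a three-knot spline so that "the conservative rule of thumb of approximately 10 events per variable is observed".
- **Secondary binary endpoints** (total mortality, revascularization, ICD implantation). SAP B.3: "Logistic regression will be used to adjust for baseline imbalances as needed".
- **Use of the randomization strata.** SAP B.2 uses EF and revascularization to test treatment-by-stratum interaction, not to give an adjusted overall effect.
- **Protocol.** Section 1.5.6 stratifies randomization by EF (≤25% v >25%) and revascularization (None/PCI/CABG), "both known strong predictors of mortality", and by site. Section 1.5.11 still describes a primary exact test stratified by EF and receipt of PCI or CABG, and by length of follow-up.

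**The concern.** In a randomized trial a baseline imbalance is a chance event. The better reason to adjust for a variable is that it predicts the outcome. B.1 item 2 does require the variables to be prognostic, but it also requires an observed imbalance. It does not say how imbalance is measured, how large is large enough, which variables are candidates, when the check is made or who makes it. Three things are therefore settled by comparing the arms: whether an adjusted estimate is produced, what it adjusts for, and whether it uses direct terms or a propensity score.

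The trigger also tends to miss the variables the protocol itself names. Stratified blocks keep EF and revascularization close to balanced, so a rule that looks for imbalance passes over them and picks up chance differences elsewhere.

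B.1 item 3 handles the same question better. Its weighting models draw on a pre-listed set of known correlates and select among them without looking at the primary outcome. Item 2 has no such safeguard. At stake is whether the adjusted results, for an endpoint with about 38 expected events, can be read as a planned robustness check or as one chosen after seeing the data.

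**Working it through.** The plan states no figure on this point. As a check on the planning inputs, its total of 1,890 (3.0% v 1.02%, 80% power, two-sided 0.05, 2:1) is recovered to within 3%. The two-proportion formula with continuity correction gives 623 controls, 3 × 623 = 1,869 in all, or 1,908 with the unrounded vest rate of 1.037%.

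**Inputs.** Final sample size 2,300 and pooled event rate 1.66% (protocol 1.5.12); 2:1 allocation, so 1,533 and 767; limit of about 10 events per variable (SAP B.1 item 2). The number of candidates K and the meaning of substantial are not in the documents and are assumed.

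**1. Chance that the trigger fires when randomization has worked.**
- SD of a standardized difference = √(1/1,533 + 1/767) = 0.0442.
- P(|difference| > 0.1) = 2 × [1 − Φ(0.1/0.0442)] = 0.0238.
- P(at least one of K independent variables) = 1 − (1 − 0.0238)^K, or 1 − 0.95^K if substantial is read as p<0.05.

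| K | standardized difference > 0.1 | p<0.05 |
|---|---|---|
| 3 | 7% | 14% |
| 5 | 11% | 23% |
| 10 | 21% | 40% |

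The answer moves about sixfold with terms the SAP leaves undefined.

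**2. Whether EF would ever be selected.** A null simulation used 3,000 trials per scenario. It assumed 100 sites, blocks of 3 or 6, EF ≤25% in 30%, 5 or 10 further covariates, odds ratios of 1.5 or 2, and a trigger at p<0.05 or p<0.10. EF met the trigger in at most 0.13% of trials. Revascularization was not tallied separately, but it is blocked in the same way.

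**3. Effect on error rates.** In the same simulation the unadjusted test rejected in 4.4-5.7% of trials. Reporting the better of the unadjusted and triggered results rejected in 4.5-5.9%. The largest gap within a scenario was 0.3 percentage points.

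**4. Whether a fixed model is affordable.** Expected events = 2,300 × 0.0166 = 38.2.
- Arm + EF (1 term) + revascularization (2 terms): 4 parameters, 38.2/4 = 9.5 events each.
- The SAP's propensity spline (arm + 2 basis functions): 3 parameters, 38.2/3 = 12.7.
- Arm + five dummies for the six joint strata: 6 parameters, 38.2/6 = 6.4.

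Main effects for the two factors roughly meet the SAP's own rule; the six joint strata do not. Total mortality contains the primary deaths, so it cannot have fewer events.

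**The case against.** The strongest reply is that little depends on this. The primary test is fixed, item 2 is labelled a sensitivity analysis, and the simulated inflation is negligible. All of that stands.

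A second reply is that the fixed model would add little information. In a separate simulation (assumed odds ratios of 2 for low EF, 1.8 for no revascularization and 0.55 for the vest; EF ≤25% in 35%; revascularization split 15/75/10%), adding the two factors moved the treatment log odds ratio by a median of 0.002-0.009, against a standard error of about 0.33-0.35. Power changed by less than 1 point. This also stands: the gain is in pre-specification, not in precision. Removing the imbalance-driven model altogether would also discard the only planned response to chance imbalance in factors that were not stratified, so it is better relabelled than deleted.

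Three stronger readings are tempting but not supported:
- **That the trigger is close to a coin flip.** This needs 15-20 independent candidates tested at p<0.05 (54-64%). The SAP limits the trigger to powerful prognostic variables, and no section lists that many.
- **That B.3 also builds a propensity score.** It mentions only logistic regression. The score belongs to B.1 item 2, applies only to more than two factors, and is a stated way to limit parameters.
- **That the plan adjusts for post-randomization treatment.** Protocol Table 2 collects "discharge meds & diagnoses (from chart") at enrollment, and discharge can follow randomization. But the SAP restricts adjustment to baseline variables and nowhere proposes discharge medication. It is a reason to state a pre-randomization rule, not an error in the plan.

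The SAP also gives no timing for the imbalance check. That it follows unblinding is an inference, although arms cannot be compared without the assignments.

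**Conclusion.** The point holds and is minor. Under the SAP, the existence and content of the adjusted estimates depend on observed imbalance judged by no stated criterion. No unconditional estimate adjusted for EF and revascularization remains, while protocol 1.5.11 still stratifies the primary test by them.

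A reader might infer that the primary conclusion is at risk. It is not: the chi-square test does not depend on the trigger, so its type I error is unaffected. What is weakened is the credibility of the adjusted primary and secondary results, which may be absent or may look selected.

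The 7-21% and 14-40% ranges rest on 3 to 10 independent candidates and on two assumed readings of substantial. The 38 events rest on the pooled rate of 1.66% at 2,300 participants.

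**What to change.** 1. In SAP B.1 item 2, and in B.3 for total mortality, replace the conditional wording with one logistic model: arm, EF (≤25% v >25%) and revascularization (None/PCI/CABG), as used for randomization. Report it beside the unadjusted test whatever the observed balance. Firth penalization, and age for total mortality, are optional; if wanted, specify them in advance.
2. Keep any imbalance-driven model, including the propensity score, as a post hoc exploratory analysis limited to variables fixed before randomization.
3. Reconcile protocol 1.5.11 with SAP section A, so that one text states whether the primary test is stratified.

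The cost is wording only, since both factors are already recorded for randomization. The downside is that a surprising imbalance in another variable is addressed only in the post hoc model.
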